6.6.5 Transplant Period

During the transplant procedure, the subject will be monitored by continuous ECG, and pulseoxymeter as well as clinically by the transplant surgeon. Capillary blood glucose will be measured every 30 minutes.

Although daily SMPG readings will not be required while in the hospital, the subject should be instructed to continue to complete the diary with all other relevant information (i.e. adverse events).

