6.6.7 Post-Transplant Period (see Appendix Detailed Visit Schedule)

Following transplant of islet cells, subjects will monitor their own glucose levels at home. Subjects will be asked to record results in a log for review at the next study visit. Blood samples for analysis (see Appendix *Detailed Visit Schedule*) are drawn three times per

week for the first two weeks and twice a week until the end of the 10th week (see Section 6.6.8 *Schedule of Evaluation*).

Subjects will come to the Clinical Research Center for visits and tests 3 times a week for the first two weeks, then twice per week for another 2 weeks, then weekly until week 12 after transplantation, then gradually tapered to every month during the first year. Additional visits may be necessary. The last study visit will be 52 weeks after transplantation. Additional evaluations may be required for medical conditions presenting during the study period and according to best medical practice.

When a second or third transplant is completed, the follow-up visit schedule is re-started to permit careful follow-up during the immediate post-operative period. In the event a second transplant is not needed due to successful engraftment, insulin independence, and stable blood glucose levels, the follow-up schedule will be maintained at monthly intervals following week 12 through the first year study period according to the *Schedule of Evaluation* in Section 6.6.8.

As in any other transplant situation, medical conditions that arise (e.g., new serious infection, malignancy, compliance issues, etc.) will automatically trigger a re-evaluation to determine if the subject remains qualified for continuous immunosuppression and subsequent transplants, if applicable.

The following laboratories will perform analyses of blood and urine samples:

CMV antibody panel, EBV antibody panel, C-peptide, insulin, anti-islet cell antibodies, anti-IA2, anti-GAD65, and anti-insulin antibodies will be analyzed at:

*ARUP Laboratories
[name]
[name]*

CMVqPCR and EBVqPCR will be analyzed at:

*ViraCor
[name]
[name]*

Inflammatory and detailed lipid panels will be analyzed at:

*CRL Medinet, Inc.
[name]
[name]*

Autologous crossmatch and donor crossmatch will be analyzed at:

*Gift of Hope Organ & Tissue Donor Network Histocompatibility Laboratory
[name]
[name]*

PRA and HLA will be analyzed at:

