- Fasting capillary glucose level should not exceed 140 mg/dL (7.8 mmol/L) more than three times in the past week (based on measuring capillary glucose levels a minimum of 7 times in a seven day period).
- Fasting plasma glucose level \leq 126 mg/dL (7.0 mmol/L); if the fasting plasma glucose level is $>$ 126 mg/dL (7.0 mmol/L), it must be confirmed in an additional one out of two measurements.
- 2-hour postprandial capillary glucose should not exceed 180 mg/dl (10.0 mmol/L) more than three times in the past week

based on measuring capillary glucose levels a minimum of 21 times in a seven day period.

- Evidence of endogenous insulin production defined as fasting or stimulated C-peptide levels 0.5 ng/mL (0.16 nmol/L)
2. **Hypoglycemic episodes** will be measured by the number and severity of hypoglycemic episodes quantified by the Ryan HYPO Score (31) (see Appendix *HYPO Score sheets*), and the percent reduction will be reported.
 3. **Glucose variability and hypoglycemia duration will be measured by continuous glucose monitoring system (CGMS)** for a 3-day period at three different time points: 1) at screening, 2) one year after first islet transplant, and 3) one year after last islet transplant. The following measurements and analysis will be reported:
 1. Mean glucose concentration
 2. Percent of time in the following ranges:
 - < 60 mg/dl
 - 60-140 mg/dl
 - 141-200 mg/dl
 - > 200 mg/dl

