### **8.2.3 Analysis of baseline diabetes control variables**

The diabetes control variables are all continuous scale variables and will be summarized as mean, standard deviation, median, minimum and maximum.

Insulin requirement will be taken from self-reported insulin regimen on the current medication list at the point of immediate pre-transplant assessment. If a range instead of an exact dose schedule is given, the average value of the range will be used. Insulin dosing will be summarized in total units per kg per day by administration routes. If the insulin doses are

reported as units per day, the value will be divided by the patient weight (in kg) measured at the corresponding visit to derive the requirement in units/kg/day.

Reduced awareness of hypoglycemia is reported qualitatively at enrollment. The proportion of patients having reduced awareness of hypoglycemia at baseline will be summarized.

Baseline SHE frequencies will be based on records available during the time period between study enrollment and the first islet transplant. A SHE is identified as a hypoglycemic event in which the patient required assistance, including help from someone else to recognize or treat the reaction, injection of Glucagon, or use of hospital/ambulance. Additionally, either a blood glucose (BG) level under 50 mg/dL (when recorded) or recovery with juice/food/glucagon is concomitant of a SHE.

The frequency of SHE is calculated by dividing the total number of SHE by the total number of days during which the events were recorded and then multiplied by 30 to produce incidence per month. Note that the duration of time between enrollment and the first transplant may vary by patient. The frequencies of SHE will be summarized at baseline.

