Baseline hypoglycemia severity will be quantified by the HYPO Score (Ryan EA, et al., 2004). The HYPO score is a scalar quantity based on patient recording of blood glucose readings and hypoglycemic events throughout the screening period prior to the first islet transplant. A hypoglycemic event occurs when a blood sugar reading is less than 54 mg/dL and a series of self-reported questionnaire items determine the severity. Points are awarded for each occurrence of documented hypoglycemia and extra points are given depending on the neuroglycopenic symptoms experienced or lack thereof. No points are awarded if there are autonomic symptoms, even if some neuroglycopenic symptoms are also present. Additional points are given for the need of outside help to either recognize or treat the event. A patient's baseline HYPO score is computed for the complete year by dividing the total score, the sum of points awarded to each hypoglycemic event reported, by the total number of days between enrollment and initial islet infusion (up to 365 days prior to the initial infusion), and then multiplying with 365. A larger HYPO score indicates greater severity. The analysis of the raw HYPO score adopts the methods for continuous scale variable.

Baseline lab test results for all the other variables will be taken from the CRF at the immediate pre-transplant assessment, if available. If a test was not scheduled for the immediate pre-transplant work-up, then the last available lab result from the screening visit prior to the first transplant will be used to represent baseline value.

For baseline Mixed Meal Test results, the proportions of patients' fasting and 90-minute C-peptide levels not exceeding the lowest detectable limit, 0.1 ng/mL, will be evaluated. C-

peptide levels reported as less than 0.1 ng/mL will be given the value 0 for any planned analyses that involve calculations based on C-peptide measures.

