## 9.2. Analysis of Secondary Endpoints

Except for the primary analyses there are no explicit or implied hypotheses in the protocol. Changes in the secondary outcomes are of interest as they will relate to efficacy as measured by the primary outcome variable. All the secondary endpoints will be evaluated at 1 year after the first and 1 year after the last transplant, respectively, with the day of corresponding transplant always designated Day 0.

We will evaluate the proportions of patients presenting with insulin independence among all patients and among the patients who fulfilled the primary endpoint, respectively. **Insulin independence** while fulfilling the primary endpoint will be further evaluated by the following parameters:

- Absence of exogenous insulin injection reported at Day 365.
- Fasting capillary glucose level not exceeding 140 mg/dL (7.8 mmol/L) more than three times in a week (based on measuring capillary glucose levels a minimum of 7 times in a seven day period) at Day 365 ± 28 days.
- Fasting plasma glucose level ≤ 126 mg/dL (7.0 mmol/L) at Day 365 ± 28 days (if the fasting plasma glucose level is > 126 mg/dL [7.0 mmol/L], it must be confirmed in an additional one out of two measurements).
- 2-hour postprandial capillary glucose not exceeding 180 mg/dl (10.0 mmol/L) more than one out of every seven times in a week (based on measuring capillary glucose levels a minimum of 7 times in a seven day period) at Day 365 ± 28 days.
- Evidence of endogenous insulin production defined as fasting or stimulated C-peptide levels ≥ 0.5 ng/mL (0.16 nmol/L) at Day 365 ± 28 days.

Number and percent (over the total number of patients attaining primary endpoint) of patients attaining each outcome listed above will be summarized.

**Hypoglycemic episodes** will be measured by the Ryan HYPO Score (Ryan et al., 2004) derived from the number and severity of hypoglycemic episodes recorded throughout the follow-up phase from Day 28 to Day 365. Additionally the percent reduction from baseline will be reported.

**Glucose variability and hypoglycemia duration will be measured by continuous glucose monitoring system (CGMS)** for a 3-day period at three different time points: 1) at screening, 2) one year after first islet transplant, and 3) one year after last islet transplant. The following measurements and analysis will be reported:

- Mean glucose concentration
- Percent of time in the following ranges:
  - < 60 mg/dl
  - 60-140 mg/dl
  - 141-200 mg/dl

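### The percent reduction in HYPO score compares periods with different scheduled self-check rates (7/day before transplant, 4 then 2/day after), so part of it may reflect checking less often.

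*SAP*

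**What the plan says.** **Trigger and points.** SAP 8.2.3 builds the score from patient-recorded glucose readings and events: "A hypoglycemic event occurs when a blood sugar reading is less than 54 mg/dL". Severity comes from self-reported questionnaire items. Events with autonomic symptoms score nothing. "Additional points are given for the need of outside help to either recognize or treat the event".

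**Baseline scaling.** Total points are divided "by the total number of days between enrollment and initial islet infusion (up to 365 days prior to the initial infusion"), then multiplied by 365. The number of readings does not enter.

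**Follow-up.** SAP 9.2 says the one-year score is "derived from the number and severity of hypoglycemic episodes recorded throughout the follow-up phase from Day 28 to Day 365", after the first and after the last transplant, with percent reduction from baseline. It does not say what the follow-up points are divided by. Table 14.2.2b shows only descriptive statistics.

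**Self-check schedule.** Protocol 6.6.8 and SAP 17.1.1 agree: 7/day at the screening, waiting-list, transplant and week 1-2 visits; 4/day at the visits for weeks 3 to 12; 2/day at the visits for weeks 16 to 52. Protocol 6.6.7 adds: "When a second or third transplant is completed, the follow-up visit schedule is re-started".

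The text supplied contains no adjustment or sensitivity analysis for reading frequency. The HYPO score sheets and Detailed Visit Schedule appendices are present only as titles and could not be checked.

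**The concern.** A low that nobody measures cannot score through a reading. If points are divided by days while the number of checks per day falls, recorded lows fall too, even when the patient's glucose is unchanged. Taken alone, the schedule change therefore favours transplantation.

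Reliance on scheduled checks is plausible here. Reduced awareness of hypoglycemia is an inclusion criterion, and lows with autonomic symptoms score no points. The lows that do score are those least likely to prompt an extra check.

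Percent reduction in HYPO score is a named secondary efficacy endpoint in a single-arm study meant to support a license application (SAP 2.1, 2.2). No control group shows how much of a fall would come from testing less often.

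**Working it through.** The documents give no expected HYPO score or percent reduction, so there is no plan figure to reproduce.

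**Inputs.** The window is Day 28 to Day 365 inclusive: 365 − 28 + 1 = 338 days (SAP 9.2). Check rates come from Protocol 6.6.8 and SAP 17.1.1. The 7/day phase after transplant ends before Day 28, so without a re-transplant only 4/day and 2/day apply. No rate is marked between the week 12 and week 16 visits, so both switch points are shown.

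**Scheduled checks in the window**
- Switch after Day 84: 57 days × 4 + 281 days × 2 = 228 + 562 = 790; 790/338 = 2.34/day.
- Switch at Day 112: 84 days × 4 + 254 days × 2 = 336 + 508 = 844; 844/338 = 2.50/day.

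**Apparent reduction with no true change.** Assume 7/day throughout baseline, complete diaries, division by days in both periods, and points from scheduled readings proportional to the number of readings. With s the share of points that depend on scheduled readings, apparent reduction = s × (1 − mean checks per day / 7).
- s = 1: 1 − 2.34/7 = 66.6%; 1 − 2.50/7 = 64.3%.
- s = 0.5: 33.3% and 32.2%.
- s = 0.25: 16.7% and 16.1%.
- s = 0: none.

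The documents do not give s; these values are assumptions that show the range. The s = 1 figure is an upper bound, also because several checks may catch the same low episode.

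**Re-transplant.** A restart brings back 7/day and then 4/day. That raises the average check rate in the first-transplant window and lowers the bound. The last-transplant window, by definition, contains no restart.

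**Incomplete baseline diaries.** The baseline divisor is all days up to infusion, so a day without a diary entry adds to the divisor but not to the points. If a fraction c of baseline days has entries and follow-up is complete, net apparent reduction = 1 − (1 − R × s)/c, with R = 0.666. This is zero at c = 0.33 for s = 1 and at c = 0.67 for s = 0.5; below that the sign reverses. Equal incompleteness in both periods leaves the artefact unchanged.

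**Unstated follow-up scaling.** If the 338-day sum were set against the annualised baseline without scaling, 1 − 338/365 = 7.4% would appear as reduction for that reason alone.

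**The case against.** **The baseline rate is partly inferred.** The 7/day entry stands in visit columns. The waiting-list section (Protocol 6.6.3) lists its tests without mentioning self-monitoring. Protocol 6.6.5 ("Although daily SMPG readings will not be required while in the hospital") implies daily readings at home but gives no rate. This stands, and it is a condition of the bound.

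**Patients may check more often than scheduled.** The protocol's insulin-independence criteria call for fasting checks at least 7 times a week and postprandial checks "based on measuring capillary glucose levels a minimum of 21 times in a seven day period", together 28/7 = 4/day. The SAP reduces this to 7 plus 7 a week, or 2/day. One week at 4/day hardly moves the result: (790 + 14)/338 = 2.38/day, 66.0%. SAP 2.6 mentions continuous in-home monitoring but no rate. Actual readings could differ, which is a reason to tabulate them.

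**Other outcomes cover the question.** CGMS percent time below 60 mg/dL does not depend on the self-check schedule, and severe events are tabulated separately. That limits the damage, but CGMS covers only 3 days at each time point and is not used to correct the HYPO score. SAP 9.2 attaches no hypothesis to secondary endpoints, which also lowers the stakes.

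**Readings that go too far.** A reader might contrast HYPO with severe-event frequency, which is divided "by the total number of days during which the events were recorded", and infer that the latter counts only days with an event. The natural meaning is the recording period: SAP 8.2.3 bases it on records between enrollment and first transplant and notes that this length varies. On the other reading, any patient with an event would show at least 30 a month. A reader might also take the Phase 1/2 experience to show that three infusions are common. Protocol 4.1.3 reports three in only 2 of 10 subjects, both in the group without etanercept and exenatide.

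**Conclusion.** The point holds as a possible bias of unknown size. Baseline points are scaled by days, the follow-up denominator is unstated, and scheduled checks in the follow-up window average 2.34-2.50/day against 7. Part of the reported reduction may therefore come from checking less often.

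The 64-67% figure is an upper bound for no re-transplant. It requires every point to come from a scheduled reading, 7/day throughout baseline, and complete diaries. It falls in proportion to the schedule-dependent share of points.

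A reader might infer that the HYPO result is inflated by some such amount, or at least inflated. The documents support neither: the share is not given, 7/day between waiting-list visits is inferred, and incomplete baseline diaries could offset or reverse the effect. The endpoint is descriptive, and this point does not touch the primary endpoint. It is a cheap improvement to the analysis plan.

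**What to change.** In SAP 9.2 and Table 14.2.2b:

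1. Keep the HYPO score as defined in 8.2.3, and state that follow-up uses the same formula, points / days × 365.
2. Tabulate recorded readings per day and the number of days with any diary entry, for baseline and for follow-up.
3. Report outside-help points separately, since they depend less on the check schedule.
4. Add one prespecified sensitivity analysis at equal check frequency: either points per recorded reading, or baseline readings thinned to the patient's own follow-up rate where individual readings are available. Leave outside-help events unthinned. Do not try to exempt symptom-prompted checks, because nothing in 8.2.3 shows that the questionnaire records why a check was made.
5. Report percent reduction both ways, read it beside CGMS percent time below 60 mg/dL, and qualify any statement about its size if the two differ.

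The cost is SAP wording, some extra programming and possibly entry of individual diary readings, since the documents do not show that every reading reaches the database. The sensitivity analysis may give a smaller reduction, and a per-reading rate is itself affected by time of day and repeat checks. No clinical procedure changes.

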### **2.4. Main Criteria for Inclusion**

Enrolling patients must have Type 1 diabetes mellitus for more than 5 years, complicated by the following situations that persist despite intensive insulin management efforts:

- a. At least one episode of severe hypoglycemia in the past 3 years defined as an event with symptoms compatible with hypoglycemia in which the patient required the assistance of another person, and which was associated with either a blood glucose level < 50 mg/dL (2.8 mmol/L) or prompt recovery after oral carbohydrate, intravenous glucose, or glucagon administration.
- b. Reduced awareness of hypoglycemia, as defined by the absence of adequate autonomic symptoms at capillary glucose levels of < 54 mg/dL (3 mmol/L as reported by the patient).

Please see IND BB-11807 Section 6.4.2 for recipient exclusion criteria.

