### **3.1. Data Analysis**

All individual data entered into the clinical database will be presented in listings. In general, the listings will present the patients sorted by transplant number, collection day, and collection time.

Demographic, baseline characteristics, safety and efficacy variables will be summarized across the ITT population at designated time points of collection. Continuous variables (e.g., age) will be summarized using the number of observations, mean, standard deviation, median, minimum, and maximum values. Categorical variables (e.g., race) will be summarized using the number and percentage of patients in each category.

Missing data will stay missing unless an imputation rule is defined otherwise. Partially missing date/time variables will only be imputed when a derivation involving the date/time value is needed in the analysis. The imputation will be done as follows (when applicable): when the month/day is missing, July 1st will be imputed; when only the day is missing, the 15th of the month will be imputed; when time of day is the only missing element, 12:00 (out of 24 hours) will be imputed.

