#### **13.6. Individual Efficacy Response Data**

16.2.6a	Individual level of HbA1c and Hypoglycemic Events at 1 Year after First Transplant
16.2.6b	Individual Insulin Independence at 1 Year after First Transplant
16.2.6c	Individual HYPO Score and Percent Reduction from Baseline at 1 Year after First Transplant

- 16.2.6d Individual Graft Failure at 1 Year after First and Last Transplant
- 16.2.6e Individual Imputed Value and Reason for Imputation in Efficacy Evaluation

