Among patients fulfilling the primary efficacy outcome (N=X):				
Absence of exogenous insulin	X (XX)	X (XX)	X (XX)	X (XX)
Fasting capillary glucose in a week:				
Not exceeding 140 mg/dL more than 3X	X (XX)	X (XX)	X (XX)	X (XX)
Fasting plasma glucose $\leq$ 126 mg/dL	X (XX)	X (XX)	X (XX)	X (XX)
Postprandial capillary glucose in a week:				
Not exceeding 180 mg/dl more than 1X/7X	X (XX)	X (XX)	X (XX)	X (XX)
C-peptide (fasting or stimulated) $\geq$ 0.5 ng/mL	X (XX)	X (XX)	X (XX)	X (XX)

XXXXXXXXXX.sas, DDMMYYYY:HHMM

TABLE 14.2.2b  
 Summary of Secondary Efficacy Endpoints:  
 Patients' HYPO Score at 1 Year after First and Last Transplant

ITT population (N=X)		n	Mean	SD	Median	Minimum	Maximum	Missing n (%)
HYPO	Baseline (pre-Tx):	X	XX	XX	XX	XX	XX	X (XX)
	First Tx Day 365 % Reduction from baseline	X	XX	XX	XX	XX	XX	X (XX)
	Last Tx Day 365 % Reduction from baseline	X	XX	XX	XX	XX	XX	X (XX)

XXXXXXXXXXXX.sas, DDMMYYYY:HHMM

TABLE 14.2.2c  
 Summary of Secondary Efficacy Endpoints:

Patients' Glucose Variability and Hypoglycemia Duration at 1 Year after First and Last Transplant

ITT population (N=X)		n	Mean	SD	Median	Minimum	Maximum	Missing n (%)
Baseline	Mean Glucose	X	XX	XX	XX	XX	XX	X (XX)
	Percent time in range:							
	< 60 mg/dl	X	XX	XX	XX	XX	XX	X (XX)
	60-140 mg/dl	X	XX	XX	XX	XX	XX	X (XX)
	141-200 mg/dl	X	XX	XX	XX	XX	XX	X (XX)
	> 200 mg/dl	X	XX	XX	XX	XX	XX	X (XX)
First Tx Day 365	Mean Glucose	X	XX	XX	XX	XX	XX	X (XX)
	Percent time in range:							
	< 60 mg/dl	X	XX	XX	XX	XX	XX	X (XX)
	60-140 mg/dl	X	XX	XX	XX	XX	XX	X (XX)
	141-200 mg/dl	X	XX	XX	XX	XX	XX	X (XX)
	> 200 mg/dl	X	XX	XX	XX	XX	XX	X (XX)
Last Tx Day 365	Mean Glucose	X	XX	XX	XX	XX	XX	X (XX)
	Percent time in range:							
	< 60 mg/dl	X	XX	XX	XX	XX	XX	X (XX)
	60-140 mg/dl	X	XX	XX	XX	XX	XX	X (XX)
	141-200 mg/dl	X	XX	XX	XX	XX	XX	X (XX)
	> 200 mg/dl	X	XX	XX	XX	XX	XX	X (XX)

Note: Baseline levels were measured prior to the initial transplant.

XXXXXXXXXX.sas, DDMMYYYY:HHMM

TABLE 14.3.1  
 Overall Summary of Treatment-Emergent Adverse Events

Type of AE	# of Islet Transplantations Received			
	Total [1] (N=X)	1 Tx (N=X)	2 Tx's (N=X)	3 Tx's (N=X)
TEAEs				
Events	X	X	X	X
Patients: n(%)	X (XX%)	X (XX%)	X (XX%)	X (XX%)
Serious TEAEs				
Events	X	X	X	X
Patients: n(%)	X (XX%)	X (XX%)	X (XX%)	X (XX%)
TEAEs leading to discontinuation				
Events	X	X	X	X
Patients: n(%)	X (XX%)	X (XX%)	X (XX%)	X (XX%)
TEAEs with an outcome of death				
Events	X	X	X	X
Patients: n(%)	X (XX%)	X (XX%)	X (XX%)	X (XX%)

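### HYPO change is reported only as each patient's percent reduction, which is undefined at a zero baseline; those patients leave the change summary and no rule covers them

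*SAP*

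**What the plan says.** SAP 9.2 measures hypoglycemic episodes by the HYPO score over Day 28 to Day 365 and then states: "Additionally the percent reduction from baseline will be reported". Protocol 6.10.2 and SAP 2.7.2 also pair the score with a percent reduction.

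The percentage is per patient. The shell of Table 14.2.2b has an entry "First Tx Day 365 % Reduction from baseline", and a matching one for the last transplant, under columns for n, mean, SD, median, minimum, maximum and missing. Listing 16.2.6c is titled "Individual HYPO Score and Percent Reduction from Baseline at 1 Year after First Transplant". No absolute change in HYPO score is named in either document.

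The baseline score is defined in SAP 8.2.3. Points are summed, divided "by the total number of days between enrollment and initial islet infusion (up to 365 days prior to the initial infusion") and multiplied by 365. No minimum window is set. On scoring, the section says: "No points are awarded if there are autonomic symptoms, even if some neuroglycopenic symptoms are also present".

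Two missing-data rules apply. SAP 3.1 leaves missing values missing unless a rule says otherwise. SAP 9.2 lets a later evaluation stand in for an unavailable scalar endpoint; failing that, the patient stays missing.

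**The concern.** A percent reduction needs a baseline above zero. A patient with no scoring event between enrollment and first infusion has a baseline of zero, and therefore no value. That patient cannot have improved; the score either stayed at zero or rose. The Missing column gives a count but not the direction of change. A patient who got worse is thus left out of the only planned summary of HYPO change.

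A low but non-zero baseline causes a different problem. Improvement is capped at 100% while worsening has no lower bound, so one such patient can pull the mean far from what happened to the group.

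**Working it through.** **Inputs.** The documents give no HYPO values, event rates or expected reduction, so there is no stated figure to reproduce. SAP 2.8 considers 15 to 50 patients. All scores and event rates below are assumptions, used only to show the mechanism.

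**Step 1, zero baseline.** Percent reduction = 100 × (B − F)/B, with B the baseline and F the follow-up score. At B = 0 this is undefined, both for F > 0 and for F = 0. A later follow-up value, as SAP 9.2 allows, changes F and leaves the denominator at zero.

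**Step 2, can B be zero?** Yes. Eligibility asks for "At least one episode of severe hypoglycemia in the past 3 years", a longer look-back than the baseline window of at most 365 days, and no minimum HYPO score is required. If scoring events followed a Poisson process, the chance of none in D days would be exp(−rate × D/365):

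| Assumed rate | 30 days | 90 days | 180 days |
|---|---|---|---|
| 6 per year | 61% | 23% | 5% |
| 12 per year | 37% | 5% | 0.3% |

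The answer depends almost entirely on the event rate and the wait, and the documents supply neither.

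**Step 3, low baseline.** If n − 1 patients each fall by a fraction r, the mean percent reduction turns negative once the remaining patient has F/B > 1 + (n − 1) × r.

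- r = 0.9: 1 + 14 × 0.9 = 13.6-fold at n = 15; 1 + 49 × 0.9 = 45.1-fold at n = 50.
- r = 0.5: 8.0-fold at n = 15; 25.5-fold at n = 50.

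A fivefold rise (−400%) among patients who otherwise fall 90% does not reverse the mean: (14 × 90 − 400)/15 = +57% at n = 15 and (49 × 90 − 400)/50 = +80% at n = 50.

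**Step 4, the measures side by side.** All patients but one go from 1000 to 100.

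| Remaining patient | n in percent summary | Mean % reduction | Median % reduction | Mean absolute fall | Median absolute fall | % fall in group median |
|---|---|---|---|---|---|---|
| n = 15, 20 to 300 | 15 of 15 | −9.3 | 90 | 821 | 900 | 90 |
| n = 15, 0 to 300 | 14 of 15 | 90.0 | 90 | 820 | 900 | 90 |
| n = 50, 10 to 500 | 50 of 50 | −9.8 | 90 | 872 | 900 | 90 |

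The first two rows describe almost the same worsening. The mean percent reduction is −9.3% in one and 90.0% in the other, where the worsened patient is absent. The absolute change keeps all 15 and hardly moves.

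**The case against.** The case for leaving the plan alone has real force.

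- A reader might infer that HYPO benefit is judged on percent reduction alone. The text does not support this: the score is the stated measure and the percentage is additional. The extracted shell shows one entry per post-transplant time point, which may be two row labels merged in reading the PDF, so it cannot show that the follow-up score is left out.
- A reader might infer that one patient could easily reverse the result. At the planned sizes that takes the extreme worsening in Step 3. The shell also prints the median, which stays at 90% in every example, and the minimum, which would expose the outlier.
- A reader might infer that zero baselines will be common. The short-wait figures in Step 2 are assumptions. Protocol 6.9.1 says that the time from screening to first transplant may be six months or more, and the second inclusion criterion requires reduced awareness below 54 mg/dL, which is close to the scoring condition. Recruits are selected to score.
- A reader might infer that lost patients leave no trace. SAP 9.2 lists missing data by patient with reasons, and Listing 16.2.6c shows individual scores, though its title covers only the first transplant.

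All of this lowers the weight of the point. It does not supply a value or a rule for a zero baseline, and the median percent reduction, robust as it is to low baselines, still leaves those patients out.

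**Conclusion.** The point holds as a minor one. The plan's only HYPO change measure is undefined for a baseline that its own scoring rules allow. The patients lost are those who cannot improve, so the omission leans towards benefit. Its size cannot be stated, because the documents give neither HYPO values nor waiting times; it is nil if no baseline is zero. The instability of the mean is real, but the planned median largely answers it, and reversal needs roughly a 14- to 45-fold worsening in one patient if the others fall 90%. The endpoint is descriptive, with no hypothesis attached, and the primary analysis does not depend on it.

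**What to change.** In Table 14.2.2b, at both time points:

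- Tabulate baseline score, follow-up score and absolute change for all patients, zero baselines included, with the median absolute change as the main change summary.
- If an interval is given, use an order-statistic interval for the median. A signed-rank interval should be labelled as Hodges-Lehmann, since it covers the median only if the changes are symmetric.
- Give the percent reduction of the group median as the percent figure.
- Keep individual percent reduction as supportive, led by its median.
- Report the number with a zero baseline and their follow-up scores.

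Absolute change needs both scores on one time scale, so SAP 9.2 should also say whether the follow-up score is annualized as the baseline is.

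The cost is a few sentences of SAP wording and one or two extra table rows. No new data are needed.
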